5.3 Benefits

While there is no direct benefit anticipated for patients in this study, the study may lead to advantages for them because of the improved resolution of imaging being offered by MRI which would not otherwise, in some cases, be performed. The study also spares patients two separate visits for a pelvic MRI, and abdominal CT, when an MRI would otherwise have been ordered.

There may be a benefit for further patient populations in that the investigators create knowledge about the performance of the PET-MRI as a one stop exam for these diseases.

5.4 Alternatives to Participation

This study does not involve a change to the standard clinical care of the participant, except for additional imaging time. There will be no consequences to individuals who withdraw or step down from the study. The subject will not undergo the PET-MRI imaging sequences if he/she refuses to take part in the study. Only the clinically indicated diagnostic PET-CT and, if requested, MRI will be performed. If a subject withdraws during the procedure of the study, the investigators will use the data as acquired up to the point of withdrawal.

5.5 Data and Safety Monitoring

Data and safety monitoring of subjects enrolled in the study will be performed by the principal investigator (PI) and co-investigators. All of the patients will be informed about the minimal risks related to their diagnostic PET-MRI study.

6.0 STUDY PARAMETERS

The study parameter is the PET-MRI data. The results of the analysis of this data (MRI findings, SUV, etc.) will be reported using special spreadsheets designed for this

purpose and will be introduced into an electronic database (REDCAP) using the code given to the patient as the only PHI.

7.0 CORRELATIVE STUDIES (if applicable)

This study is not designed as a correlative study.

8.0 STATISTICAL CONSIDERATIONS

The sample size was determined by the number of patients Philips Healthcare® has agreed to fund and is acceptable for a pilot study. Continuous variables will be expressed as mean \pm standard deviation. Comparisons between continuous variables will be performed by using the Student *t* test. Comparisons between qualitative variables will be performed by using the χ^2 test with the Yates' correction or McNemar's test as appropriate.

Sensitivity, specificity, positive and negative predictive values, and accuracy for PET-CT and PET-MRI with their 95% confidence interval will be calculated by using the standard formulas according to the criterion standard. Concordance between PET-CT and PET-MRI techniques will be assessed by using the McNemar test that evaluates whether the discrepancies between both techniques are higher than those observed by chance alone.

All calculations and statistical parameters will be calculated using Systat, Ver. 13.05 (Systat Software, Chicago, IL) or MedCalc Software, Ver. 12.3 (MedCalc Software bvba, Brussels, Belgium).

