1.0 BACKGROUND AND RATIONALE

Colorectal cancer is the 2nd leading cause of cancer related deaths in the US(1). Colon cancer accounts for 71% and rectal cancer for the remaining 29%(2). Treatment for both entities is primarily surgical with a 90% survival at 5 years when diagnosed in a localized stage, 70% for regional and 10% for metastatic disease(3). Imaging plays a crucial role in the diagnostic workup of these diseases. Both, CT and MR, have their roles in diagnosis and initial staging of both colon (CT colonography) and rectal cancer (Pelvic MR). Furthermore they also contribute substantially in follow up and restaging, along with PET-CT.

Determining T and N staging of rectal cancer is mainly done with MR given its superior tissue resolution over CT and PET-CT(4, 5). In particular for T staging similar accuracy was reported when comparing endoscopic ultrasound and MRI in cases of histologically proven rectal cancer (4). While T2 weighted sequences give a detailed anatomy and reach of the lesion as well as morphologic data regarding lymph nodes of the area, DWI sequences helps evaluate the cellular composition of both the tumor and lymph nodes showing as hyperintense lesions those with a high cellular component. On the other hand, PET-CT is used mainly in aggressive, or high grade, rectal cancer and locally advanced stages because of its high sensitivity depicting metastatic disease which might either change the therapeutic approach or suspend unnecessary interventions(6, 7). The diagnostic accuracy of PET/CT for M staging is higher than that of CT alone.

Follow up in successfully treated patients, both in colon and rectal cancer, contributes to increased survival rates, as it has been proven that patients undergoing liver imaging during follow up have a 25% lower mortality rate(8). While CT is the image modality of choice, because of availability and price, MR is more sensitive for detecting and classifying liver lesions(9) while PET-CT is more sensitive in detecting extrahepatic disease(10).

Given the obvious advantages, described above, of both MR and PET-CT in staging, follow up and restaging of these diseases, it is our objective to test the performance of PET-MRI in these diseases since it is our belief that this hybrid imaging modality will prove superior to current single imaging modality options, namely MRI, CT and PET-CT.

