3.0 PATIENT/SAMPLE SELECTION

Every patient that is scheduled to get a PET-CT at UH Case Medical Center either for preoperative high-grade rectal cancer or for colorectal cancer follow-up will be invited to join this pilot study. Initially, 10 patients per group will be invited to participate. We expect to recruit this number of patients in a two year period at the most.

Inclusion Criteria:

- Either having a T3 (The cancer has grown through the muscularis propria and into the outermost layers of the colon or rectum but not through them) or higher, node positivity or metastatic lesion in the context of rectal cancer or being studied for colorectal cancer follow up, independent of the renal function
- PET-CT should be requested by a referring physician. In the case of having an MR requested as well, it will be reported from the MRI images generated in the PET-MRI
- Stable physical medical conditions to undergo a MRI

- Informed consent must be given and signed prior to study enrollment
- Patient should be over 21 years old

Exclusion Criteria

- Refuse to give and/or sign the informed consent
- Subjects who do not meet the above mentioned inclusion criteria
- Subjects who have a pacemaker
- Subjects who have a metallic prostheses either in the pelvis or in the abdomen that will interfere with the MR imaging of that anatomical area
- Subjects who suffer from claustrophobia
- Pregnant women
- Cognitive impairment that affects the subjects ability to give consent

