5.0 RESEARCH PLAN

5.1 Study procedures and data analysis plan

Patients who enroll in this study will receive their clinically requested diagnostic PET-CT and a PET-MRI. When a diagnostic MRI is additionally requested, a report will be generated from the MRI images obtained in the PET-MRI. Both exams will be performed at the Seidman Cancer Center as part of their normal diagnostic care and will meet all of the institutionally imposed criteria for these studies. For research purposes, additional MR sequences that are completely harmless to the patient, but haven't yet been FDA approved for the clinical arena, will be performed. If any additional relevant information is discovered because of these latter sequences proper communication of these findings to the referring physician will be done.

Using the same F18-FDG injection PET-MRI will be performed, before or after the clinically requested PET-CT. If an MRI has also been requested, the report will be generated from the MRI images performed in the same scanner as the PET-MRI. After completion of the first scan, be it the PET-MRI or the PET-CT, the patient will immediately undergo the other examination. No additional F18-FDG injection will be required. MR contrast agents may be injected if it's requested by the referring physician and there are no contraindications. As a preparation for the MRI examination, all subjects except those with prior rectal surgery will receive a small amount of rectal gel to allow enhanced lesion detection. Intramuscular glucagon (1 mg) will be administered to all subjects to help relax the bowels during the MRI examination, unless there are contraindications to it which include history of glucagon hypersensitivity or pheochromocytoma. If the MRI is clinically ordered, the rectal gel and glucagon administrations are standard of care. However, they are research if the MRI is not ordered by the referring physician.

The patient will be inside the PET-MRI scanner for approximately 60-90 minutes whether or not an MRI is performed.

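### Section 8 specifies no paired comparison of PET-CT and PET-MRI accuracy, and its one named between-scan test lets gains in sensitivity and specificity offset each other

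*Combined protocol and SAP*

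**What the plan says.** The design is paired (Section 5.1): "Patients who enroll in this study will receive their clinically requested diagnostic PET-CT and a PET-MRI". The background (Section 1.0) states the expectation: "it is our belief that this hybrid imaging modality will prove superior to current single imaging modality options, namely MRI, CT and PET-CT". Section 2.0 sets the objective as the diagnostic performance of PET-MRI in two settings, preoperative staging and follow-up.

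Section 8.0 then gives three relevant items:

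- **Per-scan accuracy.** "Sensitivity, specificity, positive and negative predictive values, and accuracy for PET-CT and PET-MRI with their 95% confidence interval will be calculated". These estimates are made against the reference standard, and this is the only place in Section 8 where that standard enters.
- **A McNemar test of concordance between the two techniques.** It is described as a test that "evaluates whether the discrepancies between both techniques are higher than those observed by chance alone". The sentence mentions neither the criterion standard nor correct versus incorrect calls.
- **A general sentence on qualitative variables.** It allows a Yates-corrected chi-square or McNemar's test, whichever is appropriate, and names no variable.

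On size, Section 3.0 says "Initially, 10 patients per group will be invited to participate" and Section 8.0 says "The sample size was determined by the number of patients Philips Healthcare® has agreed to fund and is acceptable for a pilot study". No effect size, power, alpha or prevalence is stated.

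**The concern.** When each patient has both scans, the informative between-scan result is the paired difference in sensitivity among reference-positive patients and in specificity among reference-negative patients. Section 8 specifies neither. Two separate intervals cannot stand in for it, because they carry no information on how often the scans disagreed in the same patient.

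The named concordance test does not fill the gap. On positive and negative calls in all patients, a true positive and a false positive seen only on PET-MRI fall in the same cell. The test could therefore report no difference although PET-MRI was right in every discordant patient, or a difference although PET-MRI merely over-called. It also compares the sizes of the two discordant cells rather than the amount of disagreement, so a non-significant result shows neither agreement nor equal accuracy.

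At stake is what the pilot can hand to a larger study: the paired interval and the discordant counts by disease status are not specified outputs.

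**Working it through.** The plan states no power or effect size, so there is no figure of its own to reproduce. The check is of the mechanism. From the documents: both scans in every patient (5.1), 10 patients per group (3.0), the analyses in 8.0. Assumed: exact two-sided McNemar test at 0.05, and the accuracies and prevalences shown.

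**1. Where gains go.** Let *b* = PET-MRI positive, PET-CT negative, and *c* = the reverse, over all patients. A sensitivity gain for PET-MRI adds to *b*; a specificity gain adds to *c*. With N patients and prevalence π,

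E(*b* − *c*) = N[π·ΔSe − (1 − π)·ΔSp].

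This is zero when π·ΔSe = (1 − π)·ΔSp, that is, when the net numbers gained in the two strata are equal.

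**2. Small example.** Take 5 diseased and 5 disease-free patients. PET-MRI alone is right in 3 of each, and the scans agree elsewhere. The all-patient table has *b* = 3, *c* = 3, p = 1.0, although PET-MRI was right in all 6 discordant patients. Conversely, 6 false positives seen only on PET-MRI give 6 v 0, p = 0.031, with no gain in accuracy.

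**3. How far prevalence matters.** Assume sensitivity/specificity of 60%/60% for PET-CT and 90%/90% for PET-MRI, with independent errors. In either stratum, PET-MRI alone is right with probability 0.9 × 0.4 = 0.36 and PET-CT alone with 0.1 × 0.6 = 0.06, a net 0.30. At N = 100, E(*b*) = 100[0.36π + 0.06(1 − π)] and E(*c*) = 100[0.06π + 0.36(1 − π)]:

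| Prevalence | Expected *b* v *c* | All-patient test rejects |
|---|---|---|
| 0.5 | 21 v 21 | about 2% |
| 0.7 | 27 v 15 | about 39% |
| 0.8 | 30 v 12 | about 79% |
| 0.9 | 33 v 9 | about 97% |

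At half diseased and n = 10 or 20, it rejects in 0.2% and 0.9%.

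**4. Separate intervals.** Suppose PET-MRI detects 9 of 10 diseased patients and PET-CT 4 of 10. The exact 95% intervals are 55.5–99.7% and 12.2–73.8%, which overlap despite a 50-point difference. The same margins fit discordant counts of 5 v 0 (p = 0.0625) or 6 v 1 (p = 0.125); the separate intervals are identical in both cases.

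**5. What a stratified test can do.** In the example of step 2 it gives 3 v 0 in each stratum, p = 0.25. At least 6 discordant pairs, all one way, are needed for p < 0.05 (5 v 0 gives 0.0625). Power under the accuracies of step 3 is therefore 0% with 5 patients in a stratum, and about 8% with 10.

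**The case against.** **The general sentence already permits it.** A positive call among reference-positive patients is a paired qualitative variable, so McNemar's test of accuracy is available under Section 8. A reader might infer that the plan rules out or never makes an accuracy comparison; the text does not support that. It permits one without specifying it. Likewise, running the concordance test on positive and negative calls in all patients is the natural reading, but Section 8 does not state the table.

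**Cancellation is not general.** A reader might infer that a scan better on both measures shows no difference at any sample size. That needs equal net numbers gained in the two strata. The staging group is selected for T3 or higher, node-positive or metastatic disease, so an even split is not an obvious assumption there. This stands, and it is why the range above is given.

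**The remedy brings no power.** A test on correct versus incorrect calls pooled over both strata would give 6 v 0, p = 0.031, in the small example. A reader might take that as the return on the change. It is not: the stratified test recommended here gives p = 0.25 twice, and a pooled correctness test would let a sensitivity gain hide a specificity loss.

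**The reference limits any comparison.** Section 2.0 makes PET/CT the M-stage standard and part of the recurrence standard, and uses it with MRI for local stage when pathology is missing. For M stage PET-CT is right by construction. This stands and limits the fix.

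**It is a pilot.** Superiority is a belief in the background, not a decision rule, and point differences follow from the per-scan estimates by subtraction. Both are true. The paired interval and the discordant counts are still missing, and a pilot should supply them.

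**Conclusion.** The concern holds as a gap in specification with a concrete, better alternative. Section 8 uses the criterion standard only for each scan's own estimates, and its one named between-scan analysis can offset real gains: fully with equal net gains in the two strata, partly otherwise. The size depends on prevalence. Under the assumed accuracies and independent errors, the rejection rate at n=100 runs from about 2% to about 97% over prevalences of 0.5 to 0.9. These inputs are illustrative, and n=100 is far above the planned 10 per group.

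The documents do not support saying that the trial must reach a wrong conclusion, or that a better analysis would make it confirmatory. The change should be made before analysis.

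**What to change.** Add to Section 8:

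> Within each group, PET-CT and PET-MRI results will be cross-tabulated separately in reference-positive and reference-negative patients, and the tables shown. The main between-scan result is the paired difference in sensitivity and in specificity, with a 95% CI for paired proportions (score method). Any exact McNemar test in these tables is descriptive, and no conclusion of superiority or equality will be drawn from a non-significant p-value. The comparison is made only for endpoints whose reference does not include PET/CT (for example T and N stage with pathology). Where PET/CT is part of the reference (M stage, and recurrence or local stage without pathology), only agreement is reported.

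The call that counts as positive must be stated for each endpoint so that the tables can be built.

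**Cost.** Wording and a few tables from data the study will already hold; no new patients, scans or change in care. The intervals will be wide, some endpoints will have no accuracy comparison, and the stratified test has almost no power at this size. What is gained is a valid paired estimate, with discordant counts, on which to plan a larger study.

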2.0 OBJECTIVES

Our objective is to test the diagnostic performance of PET-MRI in two different settings. The first setting is the staging of preoperative high-grade rectal cancer patients, defined by T3 stage or higher or N1 stage or higher or presence of metastasis, that are referred to PET-CT and MRI. In this population Pathology will be the gold standard when available for local staging and PET/CT for M staging. When Pathology is not available, both MRI and PET/CT results will be used to determine T and N stage.

The second setting is the follow up of colorectal cancer patients that are referred to PET-CT with or without a diagnostic MRI request by their physicians. In this second group the gold standard for recurrence will be obtained from analyzing CEA levels and PET/CT and MRI results. Pathology results will be used as well whenever available.

A secondary objective is to test different attenuation correction MR sequences and novel diagnostic MR sequences.

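### Does leaving the 95% confidence interval method unnamed undermine the accuracy results at about 10 patients per group?

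*Combined protocol and SAP*

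**What the plan says.** Section 2.0 sets the aim: "Our objective is to test the diagnostic performance of PET-MRI in two different settings". The settings are preoperative staging of high-grade rectal cancer and follow-up of colorectal cancer.

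Section 3.0 gives the size: "Initially, 10 patients per group will be invited to participate". Section 8.0 gives the reason for it: "The sample size was determined by the number of patients Philips Healthcare® has agreed to fund and is acceptable for a pilot study". No expected accuracy, precision target or power is stated.

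Section 8.0 lists five measures for each modality. Sensitivity and specificity come first, and the sentence goes on: "predictive values, and accuracy for PET-CT and PET-MRI with their 95% confidence interval will be calculated by using the standard formulas". On software it says "All calculations and statistical parameters will be calculated using Systat, Ver. 13.05", with MedCalc as the alternative. No interval option is given for either package. The section does name its tests: Student t, chi-squared with Yates' correction, and McNemar.

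The unit of analysis is not stated, and neither is the cut between positive and negative for T or N stage.

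**The concern.** The five accuracy measures answer the study's main objective directly. With one result per patient, each group's accuracy rests on about 10 observations. Sensitivity and specificity share those observations between them.

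At that size the choice of interval matters. The textbook Wald interval collapses to zero width when every case is correct, and it runs past 100% just below that point. A reader could then see a perfect score in 5 or 10 patients published with no apparent uncertainty. Section 8.0 names its tests but not its interval method, so the omission stands out, and the wording does not rule Wald out.

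A related worry concerns the staging group. Patients enter with T3 "or higher, node positivity or metastatic lesion in the context of rectal cancer", so those below T3 may be few and a T-stage specificity could rest on very small counts.

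**Working it through.** The plan gives no figure to reproduce. The check asks how much the interval method could matter, and then whether the plan commits to a bad one.

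**Inputs.** n = 10 per group (Section 3.0) and a 95% level (Section 8.0). Three things are assumed because the documents give no values: true accuracies of 80%, 90% and 95%; a denominator of 5 for a measure that uses half a group; and one result per patient.

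**Formulas.**
- Wald: p ± 1.96 × √(p(1 − p)/n).
- Exact (Clopper-Pearson): limits from beta quantiles. When all n are correct, the lower limit is 0.025^(1/n).
- Wilson: the score interval. When all n are correct, the lower limit is n/(n + 1.96²).

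**Limits.**
- 10/10: Wald has p(1 − p) = 0, so 100% to 100%. Exact lower limit 0.025^(1/10) = 69.2%. Wilson 10/13.84 = 72.2%.
- 5/5: Wald 100% to 100%. Exact 0.025^(1/5) = 47.8%. Wilson 5/8.84 = 56.6%.
- 9/10: Wald 0.9 ± 1.96 × √(0.09/10) = 0.9 ± 0.186, so 71.4% to 108.6%. Exact 55.5% to 99.7%.
- 4/5: Wald 44.9% to 115.1%. Exact 28.4% to 99.5%.

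Zero width at 0% or 100% is a property of Wald at any n. A small sample only makes such a result more likely and the hidden uncertainty larger.

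**Chance of a 100% result, pⁿ.** At true 80/90/95%: 10.7/34.9/59.9% with n = 10, and 32.8/59.0/77.4% with n = 5.

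**Actual coverage of nominal 95% intervals, by binomial enumeration.** Example: n = 10, true 90%. The Wald interval contains 0.90 only when 6 to 9 are correct. Coverage is therefore 1 − P(10) − P(5 or fewer) = 1 − 0.3487 − 0.0016 = 65.0%.

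| n | True value | Wald | Exact | Wilson |
|---|---|---|---|---|
| 5 | 80% | 66.6% | 99.3% | 94.2% |
| 5 | 90% | 40.1% | 99.1% | 91.9% |
| 5 | 95% | 22.5% | 97.7% | 97.7% |
| 10 | 80% | 88.6% | 99.4% | 96.7% |
| 10 | 90% | 65.0% | 98.7% | 93.0% |
| 10 | 95% | 40.0% | 98.9% | 91.4% |
| 20 (groups pooled) | 80% | 92.1% | 97.9% | 95.6% |
| 20 (groups pooled) | 90% | 87.6% | 98.9% | 95.7% |
| 20 (groups pooled) | 95% | 63.9% | 98.4% | 92.5% |

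Wald would therefore be a poor choice here.

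**Does the plan choose it?** Nothing in the document mentions Wald, a normal approximation or a standard-error formula for a proportion. In Section 8.0 one phrase covers both the point estimates and their intervals. For the point estimates it plainly means the usual ratios from a two-by-two table. For the intervals, the exact binomial is as standard as Wald. Naming two packages does not settle the matter, because the document does not say what either would produce. All that the text establishes is that the method is unnamed.

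**What depends on it?** No accuracy hypothesis, success threshold or stopping rule refers to an interval. The point estimates and the McNemar comparison of the two modalities are the same under any interval method.

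**The staging side issue.** If 70/80/90% of 10 patients were T3 or above (an assumption), 10 × (1 − 0.7), 10 × (1 − 0.8) and 10 × (1 − 0.9) give 3, 2 or 1 below T3. Two correct out of two has an exact lower limit of 0.025^(1/2) = 15.8%. That is thin, but the cause is who is enrolled, and no interval method changes it.

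**The case for a change.** The strongest opposing case is that an unnamed method can be chosen after the results are seen. Pilot status excuses a small sample but not an interval that fails at that size. Section 1.0 states the belief that PET-MRI will prove superior, so honest intervals are the main guard against over-reading. Perfect scores are not remote either: Section 2.0 makes PET/CT the standard for M staging, so PET-CT judged against it would score 100% by construction. Naming a method would take one sentence and cost nothing.

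Much of this stands. The omission is real, the Wald figures are correct, and pooling to 20 does not rescue Wald. A named method would be tidier.

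It does not show a fault in the plan. The harm arises only if the analyst picks the one common interval that visibly breaks down at this size. Limits of 100% to 100%, or above 100%, in a table of 10 patients give themselves away, and a reader who has the counts can recompute the interval in a moment. Between the sensible choices the stakes are smaller: exact and Wilson lower limits are 69% and 72% at 10/10, and 48% and 57% at 5/5. Neither is uniquely right. Exact is conservative, and Wilson coverage can dip to about 83% for some true values at these sizes.

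The M-staging example points to a different matter. Where a test serves as its own reference, an exact interval of 69% to 100% says no more than a zero-width one. The same holds where pathology is missing: "When Pathology is not available, both MRI and PET/CT results will be used to determine T and N stage". Interval wording does not touch that.

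**Conclusion.** No change follows. Section 8.0 leaves out a detail; it does not prescribe a wrong method. Followed with exact or Wilson intervals, the plan as written gives usable limits: at least 97.7% coverage for exact and 91% to 98% for Wilson, at n of 5 or 10 and true values of 80%, 90% and 95%. The large discrepancies (69% against 100% for the lower limit at 10/10, and 65% coverage at a true value of 90%) appear only if Wald is used, which the document does not say.

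The missing unit of analysis and T/N cut-points are likewise undefined details, and a table of over- and under-staging would be a reporting preference. None of these makes a stated rule give a wrong answer in a descriptive pilot whose size was set by funding.

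This conclusion assumes that the analyst uses an interval suited to small counts and that the report shows numerators and denominators. Both are ordinary practice at this size. If a published table did show zero-width intervals, that would be a fault in the report, and it could be corrected from the same counts.

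### McNemar's test is assigned to concordance between PET-CT and PET-MRI, but it does not measure agreement or test it against chance

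*Combined protocol and SAP*

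**What the plan says.** Section 8.0 names one method for concordance between the two scans, the "McNemar test that evaluates whether the discrepancies between both techniques are higher than those observed by chance alone". It also lists McNemar, separately, among the tests for comparing qualitative variables. It further plans "Sensitivity, specificity, positive and negative predictive values, and accuracy for PET-CT and PET-MRI with their 95% confidence interval", each calculated against the criterion standard. No kappa, percent agreement or other direct measure of agreement between the scans is named anywhere.

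Section 2.0 sets the criterion standard by endpoint. For staging: "In this population Pathology will be the gold standard when available for local staging and PET/CT for M staging". Failing pathology: "When Pathology is not available, both MRI and PET/CT results will be used to determine T and N stage". For follow-up patients, "the gold standard for recurrence will be obtained from analyzing CEA levels and PET/CT and MRI results", supplemented by pathology where it exists.

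On size, section 3.0 states: "Initially, 10 patients per group will be invited to participate". Section 5.1 has each patient undergo both scans on one tracer injection, so the readings are paired.

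**The concern.** McNemar's test uses only the patients on whom the scans disagree, and compares the number positive on PET-CT alone with the number positive on PET-MRI alone. Its null hypothesis is that the two scans have equal positivity rates. The amount of disagreement does not enter that hypothesis, and neither does the agreement expected by chance. The description in section 8.0 is about amount, so it describes a different test.

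As planned, the concordance result cannot tell good agreement from poor. A non-significant p-value would be read, on the plan's own wording, as discrepancies no greater than chance. With 10 patients per group non-significance is likely to be common, so that misreading is a practical risk.

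**Working it through.** The plan states no discordance rate, agreement target or significance level, so there is no figure of its own to reproduce. The group size of 10 is from section 3.0. The cross-tables below are assumptions, and two-sided 0.05 is assumed.

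**Notation.** a = both scans positive, b = PET-CT only, c = PET-MRI only, d = both negative, n = a+b+c+d.
- Percent agreement = (a+d)/n.
- Kappa = (po − pe)/(1 − pe), with po the observed agreement and pe = [(a+b)(a+c) + (c+d)(b+d)]/n².
- Exact McNemar p = two-sided binomial probability of the b to c split with probability 1/2, taken as 1 by convention when b+c = 0.

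**1. The p-value does not track agreement.**

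| a/b/c/d | n | Agreement | Kappa | Exact p |
|---|---|---|---|---|
| 5/0/0/5 | 10 | 100% | 1 | 1 |
| 3/2/2/3 | 10 | 60% | 0.20 | 1 |
| 0/5/5/0 | 10 | 0% | −1 | 1 |
| 5/5/5/5 | 20 | 50% | 0 | 1 |
| 4/6/0/0 | 10 | 40% | 0 | 0.031 |
| 94/6/0/100 | 200 | 97% | 0.94 | 0.031 |

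Complete agreement, chance-level agreement and complete disagreement all give p = 1. A 6 to 0 split gives p = 0.031 whether agreement is 40% or 97%.

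**2. Do the planned accuracy figures fill the gap?**

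*M staging.* PET/CT is the reference, so PET-MRI is correct exactly when it matches PET/CT. Its accuracy is (a+d)/n, which is percent agreement. No gap here.

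*T and N without pathology, and recurrence.* PET/CT is one component of the reference, so accuracy overlaps with agreement only in part.

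*T and N with pathology, read as a binary endpoint.* The scans disagree when exactly one of them is wrong. If each is wrong in e of n patients and s of those errors are shared, the number discordant is 2e − 2s. Accuracy fixes e but not s. With e = 2 and n = 10, agreement lies between 60% and 100%; with e = 1, between 80% and 100%.

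Illustration (assumed): 10 patients, 6 reference-positive, each scan missing 2 positives and no negatives. Whatever the overlap, each scan has sensitivity 4/6 = 67%, specificity 4/4 = 100%, PPV 4/4 = 100%, NPV 4/6 = 67% and accuracy 8/10 = 80%. In every row pe = (4×4 + 6×6)/100 = 0.52.

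| Shared misses | a/b/c/d | Agreement | Kappa | Exact p |
|---|---|---|---|---|
| 2 | 4/0/0/6 | 100% | 0.48/0.48 = 1 | 1 (convention) |
| 1 | 3/1/1/5 | 80% | 0.28/0.48 = 0.58 | 1 |
| 0 | 2/2/2/4 | 60% | 0.08/0.48 = 0.17 | 1 |

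The outer rows are the extremes at this accuracy, 40 percentage points apart.

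**3. What non-significance can hide.** With all discordance in one direction, exact p = 2 × (1/2)^m for m discordant patients: m = 5 gives 0.0625 and m = 6 gives 0.031. So at least 6 of 10 patients must be discordant before p < 0.05 is possible, and disagreement in half a group can never reach it. The plan does not say which form of the test it will use. The uncorrected chi-square can reach significance at 4 to 0 (p = 0.046), but a 4 to 1 split gives (4 − 1)²/5 = 1.8, below 3.84, so half the group can still disagree without a significant result.

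**The case against.** The strongest defence has four parts.

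*The wording is loose, not wrong.* It might mean whether the discordant patients split more unevenly than chance would give. That would describe McNemar correctly, but concordance would still be unmeasured.

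*The plan is not blind to agreement.* This stands in part. A reader might infer that nothing planned speaks to agreement, or that every planned output would be identical in the illustration. The documents support neither. M-stage accuracy already is percent agreement with PET/CT, and accuracy bounds agreement for other binary endpoints. The illustration holds only the accuracy figures and the exact p-value constant, and its 40-point gap is the extreme. Section 8.0 plans other comparisons, section 6.0 collects SUV, and the plan does not say that only a p-value will be reported.

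*McNemar has a proper use here.* This stands. A reader might infer that it should be dropped, or barred for M staging. Comparing paired positivity rates needs no reference standard and is valid for any endpoint, so its separate listing for qualitative comparisons is not at fault. What PET/CT as reference undermines is a comparison of sensitivity or specificity, because PET/CT is then correct by definition.

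*It is a small pilot.* The sample was set by funding, and intervals will be wide under any method. That limits the importance of the point. It also favours description over testing.

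**Conclusion.** The point holds for the use and description of McNemar's test as a measure of concordance. That error follows from the definition of the test and does not depend on the assumed tables. The sizes do: 100% against 60% agreement with identical accuracy figures rests on 10 patients, a binary endpoint, a reference independent of both scans and opposite extremes of error overlap. The 6-patient threshold rests on the exact test at two-sided 0.05.

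A reader might infer that the trial's main result is compromised. Section 2.0 does not support that: its objectives are diagnostic performance and, secondarily, the testing of MR sequences. Concordance is not a stated objective and no decision rule depends on it. The sponsor should correct the plan, but what is affected is how one planned result can be read.

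**What to change.** In section 8.0:

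1. Delete the description of McNemar as a comparison of discrepancies with chance.
2. For concordance, report the paired PET-CT by PET-MRI cross-table and overall percent agreement with an exact 95% CI, per patient, per endpoint and per group. For M staging, note that percent agreement and PET-MRI accuracy are the same number.
3. For binary endpoints, where counts allow, add positive agreement 2a/(2a+b+c) and negative agreement 2d/(2d+b+c), which treat neither scan as the reference. For T and N stage, add exact-category agreement. Kappa, weighted for ordinal stage, is optional.
4. Keep McNemar, in exact form, only as a test of a difference in paired proportions: positivity rates for any endpoint, or sensitivity and specificity where the reference includes neither scan. A reference built partly from MRI may include PET-MRI, since for a requested MRI "it will be reported from the MRI images generated in the PET-MRI". Report the difference with its CI.
5. State that a non-significant McNemar result is not evidence of concordance.

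If T or N is dichotomised, the SAP must choose the cut-points. The staging group, "defined by T3 stage or higher or N1 stage or higher or presence of metastasis", is an eligibility definition and does not supply analysis thresholds. Because of that selection, few readings may be negative: 9 both positive and 1 discordant gives 90% overall but 0/(0+1) = 0% negative agreement, and 10 both positive leaves it undefined. The cross-table should therefore always be shown.

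Cost: no new data or patients, slightly more analysis, and wide intervals (8 of 10: 44 to 97%; 9 of 10: 55 to 99.7%).
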